To describe and understand barriers and facilitators to implementation in the VA context and to further assess Reach and Implementation dimensions, we will assess for any systematic differences in recruitment and retention due to age, gender, ethnicity, geographic distance from the medical center, amputation level, or marital status. Additionally, investigator-level study staff (Drs. [name], [name], [name]) will conduct structured interviews with the site coordinators and each of the VETPALS facilitators in the program at the study conclusion to assess the time commitment required to lead each group, the administrative procedures used (i.e., clinic and procedure codes, scheduling strategies), and any local clinical or organizational factors that facilitated or hindered recruitment, scheduling, retention, or delivery of the intervention. To understand better any barriers and facilitators to implementation from the Veteran's perspective, we will conduct 2-4 focus groups in the final year of the study. Participants in the focus groups will be non-randomly selected to ensure good representation of participant demographics, health status, geographic distribution, and varying levels of intervention engagement and attendance. Focus groups will be facilitated by Investigator level staff using guided questions to ascertain treatment, psychological, organizational and logistical factors that may have affected participation.

To understand the causal events leading to change and the specific components of the intervention that most influenced it, we will solicit feedback from the intervention participants, control participants, and leaders via the focus groups described above. All participants, including those participating via telehealth, may be invited. We will conduct in-person focus groups which may include participants via telehealth. We will also ask all intervention participants to complete a questionnaire via pencil-and-paper to formally assess treatment satisfaction (the same satisfaction items used in the original PALS study).

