Session 5: 2 hour class	Maintenance of self-management behaviors -Set goals for the future -Maintaining everyday life/health self-management activities -Prevention relapse

The cohorts assigned to the individual education support program (control) will be informed of their treatment group by research personnel other than the study coordinator. Participants will have access to all of the medical and rehabilitation services they would typically receive in the normal course of amputation care (e.g. post-surgical follow-up, medical stabilization and wound healing, rehab for functional independence, prosthetic fit, gait training). This includes other VA Amputation System of Care resources such as caregiver and amputee support group. Participants will not receive the VETPALS or original PALS intervention during their time in the study. To enhance usual care and encourage study participation, participants in the control condition will be systematically contacted by a clinical member of the research team and provided with post-amputation education materials. We will use one or more of the following: *First Step – A Guide for Adapting to Limb Loss* and *SideStep – A Guide to Preventing and Managing Diabetes and Its Complications* published by the Amputee Coalition and *The Next Step – The Rehabilitation Journey After Lower Limb Amputation*, a VA/DOD publication. Participants will receive a subsequent call confirming receipt of the patient education materials, and inquiring about questions associated with the information. Individuals who express an interest in additional information will be referred to their amputation care team for appropriate follow-up. All contact in the control condition will take place on an individual basis. Upon completion of the study protocol, all Veterans in the individual education support program will be offered the VETPALS program.

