Participants will be randomized to a treatment group (group-based program/intervention vs. individual education program/control) following completion of the baseline assessment (see 5.1 Study Design). The site study coordinators will be naïve to treatment allocation throughout all of the assessments to minimize potential bias of the outcomes.

Group based self-management program (VETPALS Intervention)

Participants randomized to the intervention group will be asked to complete a checklist about their use of supplementary class resources, a checklist about their satisfaction with the classes, and selected participants will be invited to participate in a focus group to respond to and discuss implementation variables. The site PIs and VETPALS facilitator have primary responsibility in overseeing data collection on paper forms. Data will be entered into the central study database by the site PIs and/or VETPALS facilitator via eCRF. In the event a participant doesn't receive

any necessary materials during class sessions, a facilitator will mail materials to the participant and will include a return postage-paid addressed envelope if needed. Participants randomized to the intervention group are offered the other program at the end of their 6-month follow-up assessment. Study coordinators will record (yes/no) patients who elect to participate in the individual program and will refer patients to the facilitator who will discuss the other program and scheduling in more detail.

We will use a digital voice recorder to audio-record the VETPALS sessions. The purpose of audio-recording the VETPALS sessions is to monitor treatment fidelity, assess feedback, and ensure protocol adherence. Each participating site will consult with the local R&D office to ensure that the digital audio-recorder meets local VA guidelines, and all recorders will use FIPS 140-2 validated encryption. Sites will use the device(s) listed in the local site Central IRB applications.

Individual education support program (Control)

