Participants randomized to the control group will not have any additional assessments or evaluations to complete. In the event a participant doesn't receive any necessary materials during the individual education support program, a facilitator will mail materials to the participant and will include a return postage-paid addressed envelope if needed. Participants in the control group are offered the VETPALS intervention classes at the end of their 6-month follow-up assessment. Study coordinators will record (yes/no) patients who elect to participate in the intervention classes and will refer patients to the facilitator who will discuss the other program and scheduling in more detail.

Patients who are randomized but unable to begin VETPALS or the Individual Education Support Program

In the event a participant is randomized but cannot begin participating in the assigned intervention, the participant will be given several options. There may be unexpected circumstances (e.g. personal or family illness, change in job status, personal situation) that may prevent a participant from starting the assigned intervention with their cohort as originally planned. VETPALS facilitators will discuss options with the participant.

1. The participant can be included in the same randomized intervention at a later date. The facilitator will wait for the next cohort that is assigned the same intervention and will contact participants to determine if they can participate with the next cohort.
2. If the participant agrees to be included in the next cohort, the facilitator will notify the study coordinator of this change so the study coordinator can include the participant in all subsequent follow-up assessments. The facilitator will only share the participant's study ID number so the coordinator remains blinded to treatment.
3. Participants may be asked to complete a second baseline assessment with the study coordinator. This will be assessed on an individual participant basis and site investigators and the PI will use their discretion when deciding if a second baseline should be completed. Collecting the baseline data again prior to starting the intervention

ensures that the research data reflects the most current responses. Participants who complete a second baseline will receive \$20 for their time and participation.

Periodic medical record review

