Use of supplementary resources will be assessed for both the intervention and control conditions by administering a brief survey coinciding with the end of the intervention sessions. The survey measures the use of supplementary project resources, including the recommended websites and participation in concurrent therapeutic/clinical activities (e.g. therapies, locally available programs such as peer visits, Amputee Support Group, and Amputee Coalition resources). This brief survey also will assess several potential factors in engagement, including perceived credibility of the treatment and perceived self-reported engagement in the treatment.

We will formally assess treatment satisfaction using a pencil and paper satisfaction measure used in the original PALS program. The VETPALS facilitator will not directly administer or collect the satisfaction measure. The Veteran peer amputee or another designee will collect all paper copies and place them in a sealed envelope. The facilitator will deliver these to the PI or Co-PI at the Seattle site either by hand delivery, secure and traceable mail (e.g. UPS), or scanning

PDF copies and uploading to a secure SharePoint. The PI and Co-PI are responsible for reviewing these questionnaires and entering data into the database.

To describe and understand barriers and facilitators to implementation of VETPALS in the VA, Investigator study staff (Drs. [name], [name], [name]) will conduct structured interviews with the site study coordinators, VETPALS facilitators, and peer facilitators at the study conclusion. These interviews will assess the time commitment required to lead each group, the administrative procedures used, and any local clinical or organizational factors that facilitated or hindered recruitment, scheduling, retention, or delivery of the intervention.

Focus Groups

To better understand any barriers and facilitators to implementation from the Veteran's perspective, we will conduct 2-4 focus groups in the final year of the study (additional details in *3.0 Objectives*). Focus groups will be facilitated by Investigator-level study staff using guided questions to ascertain treatment, psychological, and organizational and logistical factors that may have affected participation.

Staff Research Interviews

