To better understand any barriers and facilitators to implementation from the research staff perspective, we will conduct individual interviews with site study coordinators and VETPALS facilitators. Investigator-level study staff (Drs. [name], [name], and [name]) will conduct structured interviews with these staff to assess time commitment required to lead each group, administrative procedures used, and any local clinical or organizational factors that facilitated or hindered recruitment, scheduling, retention, or delivery of the educational programs.

Table 2: Assessment Timeline

See Appendix E for a copy of all measures and interview questions.

	Measure	Screening	Baseline	Treatment Completion	Month 6 Follow-Up
Screening					
Mental Status	SPMSQ	X			
Primary Outcomes					
Physical Functioning	MFA-SF		X	X	X
Psychosocial Functioning	PHQ-9		X	X	X
Secondary Outcomes					
Quality of Life	WHQOL-BREF		X	X	X
Positive Affect	PANAS		X	X	X
Intermediate Outcomes					
Self-Efficacy	MSES		X	X	X
Patient Activation	PAMS		X	X	X
Problem Solving	SPSI-R		X	X	X
SM Stages of Change	SOC		X	X	X
Prosthesis Use	Prosthesis Use		X	X	X
Potential Covariates					
Memory	RBANS		X		
Fluency/Executive Function	COWAT		X		
Attention	Digit Span		X		
Comorbidity	FCI		X		
Pain	CPG		X	X	X
Complications	Chart Review		X	X	X
Social Support	MSPSS		X	X	X
Alcohol Use	AUDIT-C		X	X	X
Smoking Status	CHQOER Ques.		X	X	X
Implementation Variables					
Treatment Engagement*	PTCS			X	
Treatment Fidelity*	Audio Recording Review		Ongoing		
Use of Supplementary Resources	Checklist			X	
Satisfaction	Checklist			X	
Implementation Barriers (Facilitator)*	Focus Group				Project Completion
Implementation Barriers (Participant)	Focus Group			Subsample	

* Completed by Study Staff

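### Focus-group invitations are not limited to participants past month 6, and Table 2 and the text disagree on when the groups are held

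*Combined protocol and SAP*

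**What the plan says.** **Timing.** Section 5.5 (Focus Groups) says "we will conduct 2-4 focus groups in the final year of the study", and section 4.0 (Aim 3) says the same. In Table 2 of section 5.5, the row that begins "Implementation Barriers (Participant" carries the entry *Subsample* in the Treatment Completion column, and its Month 6 cell is empty. The row above it, which begins "Implementation Barriers (Facilitator", carries *Project Completion* in the Month 6 column.

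**Who attends.** Section 4.0 says "we will solicit feedback from the intervention participants, control participants, and leaders via the focus groups described above" and adds "All participants, including those participating via telehealth, may be invited". Selection is purposive, and level of engagement and attendance is one of the criteria. In section 5.5 the focus group appears only under the VETPALS arm: "selected participants will be invited to participate in a focus group to respond to and discuss implementation variables". Under the control arm the same section says "Participants randomized to the control group will not have any additional assessments or evaluations to complete", and offers VETPALS to controls only at the end of the 6-month assessment. Section 5.1, describing the control programme, says "All contact in the control condition will take place on an individual basis".

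**Time points.** Hypotheses 1a and 1b cover change in MFA-SF and PHQ-9 both post-intervention and at 6 months. For hypotheses 2a–e, section 5.6 names baseline to 6 months as the primary comparison.

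**The concern.** The plan keeps the arms apart until the 6-month assessment. The focus groups are the one planned activity with no such limit. Their stated purpose in Aim 3 includes identifying which components of the intervention brought about change, so the discussion would naturally cover VETPALS content. A control who attended before month 6 would meet that content in a group. A VETPALS participant who attended would have one more group contact than the programme provides. Attendees are chosen partly on engagement, so the exposure would not be random. The survey of outside resources is given at the end of the intervention and would not record later attendance.

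What is at stake is the 6-month contrast on both primary outcomes. Exposure of controls would tend to shrink the difference between arms, while extra contact for VETPALS participants would tend to widen it.

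**Working it through.** **Inputs.** Table 1 (section 5.2): groups started per year, 8 people enrolled and 6 completing per group. Sections 4.0 and 5.5: 2–4 focus groups. Assumptions not in the documents: 6–10 people per focus group, half of attendees controls, even accrual within each year, selection in proportion to enrolment, and the final year being Year 4 of Table 1.

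**1. Reproduce Table 1.** Groups per year are 8, 21, 21 and 9, which makes 59.
- Enrolled: 59 × 8 = 472. Completing: 59 × 6 = 354. Both match.
- Year 4: 9 × 8 = 72 enrolled and 9 × 6 = 54 completing. Both match.

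**2. Does the final-year wording protect month 6?** The 72 people enrolled in Year 4 cannot have reached month 6 before that year. With even accrual, half of the Year 3 intake, 168 / 2 = 84, also has its 6-month visit in Year 4. So 72 + 84 = 156 of 472 people (33%) spend part of the final year before month 6. The wording reduces the problem but does not remove it.

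**3. Ceiling on exposure, with every attendee before month 6 (Table 2 read literally).**
- Attendees: 2 × 6 = 12 to 4 × 10 = 40.
- Share of completers: 12/354 = 3.4% to 40/354 = 11.3%.
- Controls, if half: 6 to 20 of 354/2 = 177, again 3.4% to 11.3%.

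**4. Exposure if the groups are held in Year 4.**
- Start of Year 4: enrolled 64 + 168 + 168 = 400, of whom 84 are before month 6; 84/400 = 21%.
- End of Year 4: 72/2 = 36 of 472 are before month 6; 36/472 = 8%.
- Attendees before month 6: 12 × 0.08 ≈ 1 to 40 × 0.21 ≈ 8.
- Controls, if half: about 0.5 to 4 of 177, or 0.3% to 2.4%.
- If the groups met after the last 6-month visit, the number would be zero.

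**5. Extreme bound on power.** The stated power (above 0.8 for MFA-SF) cannot be reproduced, because no effect size or SD is given. For scale only, set the effect so that power is 0.80 at two-sided 0.05, which means effect/SE = 1.960 + 0.842 = 2.802. Suppose each exposed control gains the whole VETPALS effect. The difference then shrinks by the exposed fraction f, and power = Φ(2.802 × (1 − f) − 1.960).
- f = 3.4%: Φ(0.747) = 0.77.
- f = 11.3%: Φ(0.525) = 0.70.

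Because the effect is fixed to give 0.80, the result is the same at any intra-cohort correlation from 0.01 to 0.10. One discussion would not deliver the full effect, so the real loss is smaller, and at the fractions in step 4 it is negligible.

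**The case against.** The strongest reply has four parts.

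- **Table 2 is weak evidence on timing.** Free-text entries in the same block do not follow the visit columns: *Ongoing* for fidelity falls under Baseline, and *Project Completion* falls under Month 6. The table was also read from a PDF. Two sections state the final year plainly, and 2–4 groups in total cannot be a week-6 procedure for every cohort. This stands as far as it goes: Table 2 does not show that week-6 groups are planned throughout. The mismatch remains, and so does the missing condition on month 6, which does not depend on Table 2.
- **Control-arm rules are about the programme.** The individual-contact sentence closes a paragraph on mailed materials and calls, and the 6-month rule governs when VETPALS is offered. The sentence on no additional evaluations is already loose, since sections 4.0 and 5.5 give controls the resource-use survey. This is fair for section 5.1, where the conflict is arguable. The section 5.5 sentence still contradicts control focus groups as written.
- **Group contact with peers is not withheld from controls.** Section 5.1 leaves them access to an amputee support group, and the survey records such use. VETPALS is 4 + 4 × 2 = 12 hours of taught sessions with a workbook; a focus group is a guided discussion. This stands, and it rules out describing attendance as receipt of the intervention.
- **The numbers are small, and the two arms' exposures push in opposite directions.** This stands.

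A reader might also infer that VETPALS participants, controls and group leaders sit in the same sessions. Section 4.0 lists them as three sources of feedback and does not say so. Table 2 has separate participant and facilitator rows, and sections 4.0 and 5.5 describe structured interviews for facilitators.

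**Conclusion.** The point holds as a timing gap and an inconsistency. Table 2 disagrees with sections 4.0 and 5.5 on when the participant groups meet. No section requires the 6-month assessment first, controls are expressly included, and Table 1 leaves cohorts in follow-up during Year 4. Some participants could therefore attend before a main time point for both primary outcomes.

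The size is minor: at most 12–40 attendees (3%–11% of 354), and more plausibly about 1–8 before month 6, under the group-size, accrual and selection assumptions stated above. The documents do not support reading this as planned mixing of the arms, as delivery of VETPALS to controls, or as a material threat to the trial's conclusion. It is worth correcting because the exposure is non-random, avoidable and almost free to remove.

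**What to change.** - In section 4.0 (Aim 3) and in section 5.5 (VETPALS arm and Focus Groups), limit invitations to participants whose 6-month assessment is complete or whose visit window has closed. Sections 5.1 and 5.5 give no window for that visit, so state one.
- In Table 2, move *Subsample* from Treatment Completion to after Month 6.
- In the control-arm text of section 5.5, say that controls may be invited to a focus group after month 6. Make clear in section 5.1 that the individual-contact rule applies up to that point.

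Separate sessions by arm are a matter of preference and are not needed to close the gap.

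The cost is a few sentences and one table cell. Recall of the sessions will be slightly older, and the last Year 4 cohorts may be too late to invite. Most cohorts stay eligible: at the start of Year 4, on even accrual, 400 − 84 = 316 of the 400 people enrolled by then would already have passed the 6-month point, so Aim 3 loses little.

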5.0 Resources and Personnel

Roles and responsibilities

The **Principal Investigator/Study Chair** ([name]) and **Co-Principal** ([name]), will assume responsibility for all aspects of the conduct of this research study and supervise all Seattle-based personnel. They, along with the site PIs, will be responsible for training research staff, including the VETPALS facilitators, peer facilitators, and site study coordinators. They will also develop the study protocol, operations manual, monitoring plan and have oversight on study monitoring and study steering committee meetings.

Site Principal Investigators (Drs. [name], [name], [name], [name], and [name]) are responsible for operations, data collection, and data integrity at their sites which involves oversight of the site study coordinators and regular meetings to discuss data and operations. They are also responsible for training the research staff at their site, including the VETPALS facilitator, peer facilitator, and site study coordinator. Site PIs, along with VETPALS facilitators,

will contact the data manager to obtain random assignment for participants. Site Principal Investigators may also assist with screening and enrollment as needed at their site.

Co-Investigators ([name] and [name]) will oversee VETPALS facilitator ratings on an ongoing basis to provide corrective feedback to facilitators in real-time along with the PI/SC. They will also lead weekly meetings with the study facilitators to provide ongoing supervision and discuss delivery of the treatment, including the prevention of facilitator drift in the manuals. The Co-Investigators will also assist with tasks as requested by the PI/SC, which include but are not limited to: finalizing the study protocol, overseeing progress at all sites, developing the operations manual and other study SOPs, monitor treatment fidelity by reviewing audio files, running steering committee meetings, and training VETPALS facilitators and peer facilitators.

Co-Investigator [name] was a Co-PI for the original PALS program on which VETPALS is based. He will assist with tasks as requested by the PI/SC and Co-Investigators, which include but are not limited to: training VETPALS facilitators and peer facilitators, revising the treatment manual/participant workbook, interpretation of statistical analysis, and writing manuscripts for publication at the end of the study.

Co-Investigator and Consultant [name] is responsible for all pre-study tasks and training of research staff. This includes oversight of all baseline and follow-up assessments, database development for data entry and analysis, and assistance in IRB submission. The VA Puget Sound will act as the lead study site and will host an investigators' meeting, which study site PIs, coordinators and VETPALS facilitators will attend to receive appropriate pre-study training. During this training session, the core investigators will ensure that all study materials (surveys, protocol, inclusion/exclusion criteria) are discussed, ensure that the study coordinator fully understands the study procedures and SOPs, and that all regulatory documents are approved and appropriately filed in regulatory binders. Initial training for VETPALS group facilitators will happen at this time and is described in more detail in the next section. He will also be a consultant on study operations. He will also monitor subject recruitment and follow-up rates at all sites and will monitor all adverse events.

[name] will also oversee the database manager at Spectrum Research and all database operations, including but not limited to, data queries, data analysis, data export as requested by the PI/SC. He will have primary responsibility for ensuring the safety and secure storage of all electronic study data. [name] and Spectrum Research will only have access to coded data.

Site study coordinators are primarily responsible for day to day study operations, which include recruiting participants and ensuring that all enrolled participants are adhering to the study protocol. These tasks include: ensuring all potential participants are identified through screening procedures, appropriately obtaining informed consent and HIPAA authorization, maintaining an updated screening and enrollment log, contacting participants regularly to schedule and remind them of study visits, and collecting baseline and follow-up data through the electronic data capture (EDC) system using an eCRF. The Seattle site study coordinator may also conduct study interviews by telephone for other sites in the event a site study coordinator is

unavailable. The site study coordinator will have regular contact with [name] and the site PI. The site study coordinators remain blind to treatment group.

The study **project coordinator** is based at the Seattle site, and is primarily responsible for oversight of daily study operations at the five participating sites. The project coordinator also has regular contact with [name], the PI ([name]) and Co-PI ([name]) to assist in study troubleshooting with the site PIs and study coordinators as needed. The study project coordinator, with oversight from the PI and Co-PI, is responsible for submitting IRB materials to the VA Central IRB, including but not limited to: initial applications, protocol modifications, site correspondence, protocol deviations, and SAE reports. The project coordinator, along with [name], also monitors the site study coordinators and communicates with investigators to ensure efficient day-to-day study operations. The project coordinator will organize monthly teleconferences with site PIs and study coordinators to discuss progress, operations, and answer group operational questions as they arise.

Additionally, VAPSHCS project staff will conduct periodic site monitoring and quality assurance of each site to ensure that informed consent, training requirements, and adverse event monitoring are being routinely performed in strict accordance with the research protocol, requirements of the Central IRB, and local VA R&D committees. During the first 6 months of enrollment at each site, the project coordinator and/or Drs. [name] and [name] will conduct a virtual internal audit using the regulatory audit template from VAPSHCS. We will encourage each site to conduct an internal audit that adheres to their facility audit process to confirm both project wide and local facility compliance. We will also work to request a formal R&D audit during year 1, if possible, regardless of the local policy at each site.

VETPALS facilitators are allied health professionals who are responsible for implementing the VETPALS intervention group sessions. VETPALS facilitators will be trained by the core group of investigators to deliver a modified version of PALS which reflects changes in content, delivery modalities (e.g. telehealth, video teleconferencing), and participants (Veterans with dysvascular disease/diabetes). VETPALS facilitators will receive training during a two-day group-based training that includes didactics, supervised practice, discussion, and home study. Notably, all VETPALS facilitators have already received initial training the PALS protocol and have advanced Department of Defense (DOD) training and certification in amputation care. VETPALS facilitators are primarily responsible for contacting the data manager to randomize a group of participants, maintaining an accurate randomization log, and conducting the 5 intervention sessions per group of 8 ± 2 participants. The intervention sessions will take place in a private conference room with video teleconferencing capabilities at each VA site. All VETPALS facilitators will participate in ongoing group supervision as part of fidelity monitoring of the intervention, and additional focused instruction will be provided on an individual basis as needed when identified during a review of audio-recorded sessions. VETPALS facilitators may assist with screening and enrollment at their site.

VETPALS peer facilitators are Veterans with limb loss. One peer facilitator at each site will be identified and trained by the VETPALS facilitator. Substitute or alternate peer facilitators may also receive training as needed at each site. The peer facilitator will help co-lead the VETPALS

sessions (as in the original PALS program). The peer mentor will only have study-related contact with participants in the context of the class. The peer will not access the medical record, or engage in other research-related activities. Thus, the peer mentor will not have access to any information about the participant that is not shared directly by the participant during class.

The **biostatistician** ([name]) will conduct periodic queries of the database to look for any discrepancies or inaccuracies in the data (e.g. missing and nonsensical values) that may not have picked up during the electronic data entry process. The biostatistician will primarily be responsible for statistical analysis as outlined in the original grant application and study protocol. The biostatistician will only have access to coded data.

